7.2. Definition of a Serious Adverse Event (SAE)

An SAE is any AE occurring at any dose that results in any of the following outcomes:

- a. Death.
- b. A life-threatening AE.
 - *NOTE: Life-threatening means that the Subject was, in the view of the Investigator, at immediate risk of death from the event as it occurred. This definition does not include an event that, had it occurred in a more severe form, might have caused death.*
- c. Inpatient hospitalization or prolongation of existing hospitalization.
 - *NOTE: Complications that occur during hospitalization are AEs. If a complication prolongs hospitalization, the event is an SAE.*
 - *NOTE: "Inpatient" hospitalization means the Subject has been formally admitted to a hospital for medical reasons. This may or may not be overnight. It does not include presentation at a "casualty" or emergency room.*
- d. A disability/incapacity.
 - *NOTE: The term disability means a substantial disruption of a person's ability to conduct normal life functions. This definition is not intended to include experiences of relatively minor medical significance such as uncomplicated headache, nausea, vomiting, diarrhea, influenza, accidental trauma (i.e., sprained ankle) that may interfere or prevent everyday life functions but do not constitute a substantial disruption.*
- e. A congenital anomaly in the offspring of a Subject who received drug.
- f. Important medical events that may not result in death, be life-threatening, or require hospitalization may be considered an SAE when, based upon appropriate medical judgment, they may jeopardize the Subject and may require medical or surgical intervention to prevent one of the outcomes listed in this definition. Examples of such medical events include allergic bronchospasm requiring intensive treatment in an emergency room or at home, blood dyscrasias or convulsions that do not result in Subject hospitalization, or the development of drug dependency or drug abuse.
 - Medical and scientific judgment should be used in deciding whether prompt reporting is appropriate in this situation.

7.3. Definition of an Adverse Event of Special Interest (AESI)

An adverse event of special interest (serious or non-serious) is one of scientific and medical concern specific to the sponsors program, for which ongoing monitoring and rapid

communication by the investigator to the sponsor can be appropriate. Such an event might warrant further investigation in order to characterize and understand it.

7.4. Severity of AEs/SAEs

Severity (mild, moderate, or severe) of each AE/SAE must be assessed by the Investigator or designee. The following criteria should be considered when assessing severity:

- Mild The symptom is barely noticeable to the Subject and does not influence performance or functioning.
- Moderate The symptom is of sufficient severity to make the Subject uncomfortable, and performance of daily activities is influenced. Treatment for the symptom may be needed.
- Severe The symptom causes severe discomfort. Treatment for the symptom may be necessary.

7.5. Outcome of AE/SAEs

- Not Recovered/Not Resolved: One of the possible results of an adverse event outcome that indicates that the event has not improved or recuperated.
- Recovered/Resolved: One of the possible results of an adverse event outcome that indicates that the event has improved or recuperated.
- Recovered/Resolved with Sequelae: One of the possible results of an adverse event outcome where the subject recuperated but retained pathological conditions resulting from the prior disease or injury.
- Recovering/Resolving: One of the possible results of an adverse event outcome that indicates that the event is improving.
- Unknown: Not known, not observed, not recorded, or refused.
- Fatal: The termination of life as a result of an adverse event

7.6. Assessment of Relatedness to Study Product

The Investigator will assess each AE and SAE for causality based on their best medical judgment, the observed symptoms associated with the event, and the available information on the Investigational Product (IP). The relatedness guidance provided below can be used to assist in determining the relationship of the IP to the AE or SAE. However, it is ultimately the investigator's responsibility to determine the relationship based on their best medical judgment, knowledge, and experience.

- **Not Related:** Based upon available information regarding subject history, disease process, relationship of adverse event to dosing and drug pharmacology, there is no reasonable relationship between the IP and the adverse event.
- **Possibly Related:** Relationship exists between the adverse event and IP, when the adverse event follows a reasonable sequence from the time of the IP administration,

but could also have been produced by the subject's clinical state or by other drugs administered to the patient.

- **Probably Related:** Relationship exists between the adverse event and the IP when the adverse event follows a reasonable sequence from the time of IP administration, follows a known response pattern of the drug class, is confirmed by improvement on stopping the IP and the IP is the most likely of all causes.
- **Definitely Related:** Relationship exists between the adverse event and the IP when the adverse event follows a reasonable sequence from the time of the IP administration, follows a known response pattern of the drug class, is confirmed by improvement on stopping the IP and no other reasonable cause exists.

7.7. Method, Frequency, and Time Period for Detecting Adverse Events and Serious Adverse Events

At appropriate intervals, Subjects should be assessed for AEs and SAEs as in Section 6.2.

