| INVESTIGATIONAL PRODUCT | Furosemide Injection, 80 mg per 10 mL for subcutaneous administration via the Infusor (Furoscix On-body Infusor (hereinafter referred to as Furoscix Infusor)) |
| STUDY OBJECTIVES | 
Primary Objective:
 
 Provide pilot data on effectiveness and safety to inform a pivotal trial 
Secondary Objectives:
 
 Inform population enrichment strategies Refine pivotal trial endpoints and analytical methods Identify operational challenges of study design Assess patient adherence, competence, and experience Familiarize staff and patients with device application and use |
| ENDPOINTS | 
Primary Endpoints:
 
 Improvement in a composite/combined morbidity/mortality endpoint at 30 days using the Finkelstein Schoenfeld method. 
 Cardiovascular (CV) death Heart Failure (HF) hospitalization Urgent Emergency Department (ED)/Clinic visit for worsening heart failure (defined as Intravenous (IV) diuretics, augmentation of or new administration of metolazone) Change in NT-proBNP from baseline at Day 7 Incidence of Adverse Events, Adverse Events of Special Interest, and Serious Adverse Events 
Secondary Endpoints (through 30 days):
 
 Days alive and HF event free days Global Visual Analog Scale Composite Congestion Score (CCS) 5-point Current Dyspnea Score 7-point Dyspnea Score Health-related quality of life (Kansas City Cardiomyopathy Questionnaire (KCCQ-12)) Renal Function and Electrolytes Weight Exercise tolerance (Six Minute Walking Test (6MWT)) % Lung Fluid Measurement via Remote Dielectric Sensing (ReDS) |

| | |
|------------------------------------|---|
| STUDY DURATION | 9 months |
| PARTICIPANT DURATION | 30 days |

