7. ADVERSE EVENTS

The Investigator is responsible for the detection and documentation of events meeting the definition of an AE or SAE as provided in this protocol. AEs will be assessed continuously

through the last study visit unless the nature of the AE or SAE requires continued monitoring. All AEs are recorded as mild, moderate or severe, and as Not Related, Possibly Related, Probably Related, or Definitely Related to the Investigational Product.

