7.1. Definition of an Adverse Event (AE)

An Adverse Event (AE) is any untoward medical occurrence associated with the use of an Investigational Product (IP) in humans, whether considered related to the IP. An adverse event (also referred to as an adverse experience) can therefore be any unfavorable and unintended sign (including an abnormal laboratory finding), symptom, or disease temporally associated with the use of an Investigational Product (IP) and does not imply any judgment about causality. An adverse event can arise with any use of the IP (e.g., off-label use, use in combination with another drug) and with any route of administration, formulation, or dose, including an overdose.

A “pre-existing” condition is one that is present prior to IP administration and is reported as part of the Subject’s medical history. Pre-existing conditions should be reported as AEs only if the frequency, intensity, or character of the pre-existing condition worsens during the study.

Laboratory or functional test abnormalities generally are not considered AEs unless they are associated with clinical signs or symptoms or require medical intervention. A laboratory abnormality (e.g. a clinically significant change detected on clinical chemistry, hematology, urinalysis) or functional test abnormality (e.g. a clinically significant change detected on ECG, pulse oximetry, or spirometry) that is independent from a known underlying medical condition and that requires medical or surgical intervention, or leads to IP interruption or discontinuation, must be considered an AE.

All AEs judged to be clinically significant, including clinically significant laboratory results, ECG and functional test abnormalities, will be followed until resolution or return to baseline or until no further improvement is expected.

An AE **does** include any:

- Exacerbation of a pre-existing illness.
- Increase in frequency or intensity of a pre-existing episodic event or condition.
- Condition detected or diagnosed after study product placement and/or drug administration even though it may have been present prior to the start of the study.
- Continuous persistent disease or symptoms present at baseline that worsen following the start of the study.

An AE **does not** include a/an:

- Medical or surgical procedure (e.g., surgery, endoscopy, tooth extraction, transfusion); the condition that leads to the procedure is an AE.

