8.6. Safety Analyses

Safety analysis will be performed on the safety population. No imputation will be performed for missing data. The incidence (number and percentage of subjects) of adverse events will be presented overall and by MedDRA System Organ Class (SOC) and Preferred Term (PT) for each treatment group. This analysis will be repeated for serious adverse events, for treatment-related adverse events, adverse events of special interest and for adverse events leading to premature study withdrawal.

Descriptive statistics at each time point will be presented for laboratory variables, vital signs, and body weight, stratified by treatment group.

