### **15.3 Analysis of Safety**

Descriptive statistics and appropriate tests will be used to summarize and compare the safety parameters between treatment groups. All safety analyses will be performed on the safety population. Treatment group comparisons may assess the significance of the difference between treatment and control groups.

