#### **15.3.1 Adverse Events**

Adverse events will be mapped to the Medical Dictionary for Regulatory Activities (MedDRA™) dictionary, version 23.1 . Adverse events (AE) will be summarized using number and percentage of subjects within each category of each variable overall for any AE, TEAE, serious AE, treatment related AE, AE resulting in death, AE leading to treatment discontinuation, and AE leading to study discontinuation. The incidence rates of AE will also be presented for severity, outcome, causality, and seriousness. For subjects with more than one AE within a given variable (e.g., severity), the event with the highest level of severity, outcome or causality, seriousness, respectively, will be reported. Incidence rates will also be presented for the System Organ Class (SOC) and Preferred Term (PT) of each AE. Data presented will include the number of subjects and percentage of subjects, the SOC and PT for each AE. All AEs will be presented in a listing for the Safety Population.

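### Adverse event causality is graded only against Furoscix, so the by-arm table of treatment-related events has a control column that is zero or empty by construction and should not be compared between arms

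*Protocol*

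**What the plan says.** The Protocol synopsis defines the IP as "Furosemide Injection, 80 mg per 10 mL for subcutaneous administration via the Infusor". Oral diuretics given to controls are not IP.

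Protocol 7 requires every adverse event to be recorded "as Not Related, Possibly Related, Probably Related, or Definitely Related to the Investigational Product". In Protocol 7.6 the lowest grade applies when "there is no reasonable relationship between the IP and the adverse event". Each of the three related grades needs an event that "follows a reasonable sequence from the time of the IP administration" (the middle grade differs by one article), and the two highest also require improvement after the IP is stopped. SAP 9 repeats these definitions. Neither document provides a causality rating for oral diuretics or any other assigned therapy.

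Protocol 6.2.2 puts controls on the same assessment schedule without study product. The synopsis lets the treating physician change their oral diuretic dosing.

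The analysis sections then use causality by arm. Protocol 8.6 presents adverse events for each treatment group and adds: "This analysis will be repeated for serious adverse events, for treatment-related adverse events, adverse events of special interest". SAP 15.3.1 lists treatment-related events among its summaries, does not define the term differently, and states: "The incidence rates of AE will also be presented for severity, outcome, causality, and seriousness". SAP 15.3 says: "Treatment group comparisons may assess the significance of the difference between treatment and control groups".

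Two other passages bear on this. The Safety population (Protocol 8.2, SAP 14) requires at least one dose of IP, and SAP 14 groups it by treatment actually received. Protocol 7.1 says that a laboratory abnormality which is independent of a known condition and needs intervention, "or leads to IP interruption or discontinuation, must be considered an AE".

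**The concern.** Both arms receive diuretics, and the expected harms are of the same kind. The adverse events of special interest in Protocol 3.2.3 are a creatinine rise, high or low potassium, and low magnesium. A fall in potassium after Furoscix can be graded related. The same fall after an increase in a control subject's oral diuretic cannot, because no IP was given. A table of related events by arm then reflects the attribution rule rather than a difference between treatments.

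The trial is open label, so investigators grade each event knowing the arm. Its primary objective is to supply pilot effectiveness and safety data for a pivotal trial. An excess of related events on Furoscix that arises from the grading could be carried forward as a safety signal. SAP 15 makes no adjustment for multiple comparisons, so nothing else would restrain a nominally significant result from this table.

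**Working it through.** **The plan's own figure.** SAP 4 gives 51 subjects randomized 2:1. 51 × 2/3 = 34 and 51 × 1/3 = 17, which matches the stated arm sizes.

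**Count of related events in the control column.** The three possible readings are:

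1. Controls are kept in the safety tables, as the by-arm layout of Protocol 8.6 implies. No related grade can apply without IP exposure, so the entry is 0 of 17.
2. The Safety population is read literally. Controls receive no IP dose and drop out, so the column is empty (0 of 0).
3. A control subject is given Furoscix. SAP 14 presents that subject by actual treatment, so any related event appears in the Furoscix column.

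Under none of these does the control column contain a related event.

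**Illustration of size, on reading 1.** The documents give no event rates and name no test for this table. The following are assumptions: the true proportion of subjects with a diuretic-caused event is the same value p in both arms, every such event on Furoscix is graded related, and the test is a two-sided Fisher exact test at 0.05.

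With control fixed at 0/17, 7/34 gives p = 0.080 and 8/34 gives p = 0.040. For 8 events in total:

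- All 8 on Furoscix: C(34,8)/C(51,8) = 18,156,204/636,763,050 = 0.0285.
- Opposite-tail tables that are no more probable (6, 7 or 8 of the events in controls): 0.0109 + 0.0010 + 0.0000 = 0.0120 after rounding.
- Two-sided p = 0.0285 + 0.0120 = 0.0405.

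Eight is therefore the smallest count that reaches significance. The chance of reaching it is P(X ≥ 8) with X ~ Binomial(34, p). The comparator column below is the chance of p < 0.05 if both arms were rated on the same diuretic-causality question.

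| Assumed p in both arms | Expected control events that cannot be counted (17p) | Chance of a spurious significant excess, control fixed at 0 | Chance of p < 0.05 if both arms were rated alike |
|---|---|---|---|
| 0.10 | 1.7 | 1.7% | 2.4% |
| 0.20 | 3.4 | 37% | 3.3% |
| 0.30 | 5.1 | 84% | 3.2% |
| 0.40 | 6.8 | 99% | 3.4% |

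At a 10% rate the artefact would rarely reach significance, though the displayed proportions would still be lopsided. From about 20% upward it would often do so.

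**Which outputs depend on the grading.** The primary safety endpoint is the incidence of adverse events, special-interest events and serious events (Protocol 3.2.1, SAP 10.1), with no causality condition. Special-interest events are defined by laboratory thresholds (Protocol 3.2.3, SAP 10.3). Serious and special-interest events are tabulated by arm irrespective of causality (SAP 15.3.2, 15.3.3), and laboratory data have by-arm shift tables (SAP 15.3.4). Serum creatinine also has a between-arm model on the ITT and PP populations (SAP 15.2.2). Only the treatment-related and causality tables use the grade.

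**The case against.** **The harms are compared elsewhere.** This is correct and limits the point. A reader might infer that the trial cannot show whether Furoscix causes more renal or electrolyte harm than adjusted oral diuretics. The documents do not support that, because the outputs for those harms carry no causality filter.

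**Nothing says a control event must be graded Not Related.** Also correct as to wording. Protocol 7.6 offers the definitions as guidance and leaves the decision to the investigator. What is being decided is still the relation to the IP, and one grade has to be recorded, so Not Related is the only coherent choice for an unexposed subject. That is an inference, though a strong one.

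**The illustration rests on a test nobody specified.** SAP 15.3 only permits comparisons, and Protocol 8.6 asks for numbers and percentages. Furoscix subjects also return to oral maintenance diuretics, so a later event in that arm may be graded Not Related too. The contrast is then less absolute than the illustration assumes. The figures show what the table could do and do not forecast its result.

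**IP causality is needed for its own purpose.** Protocol 7.7.2 says it may affect expedited reporting. That stands, and the rating should be kept.

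**The Safety population is the prior defect.** Read literally, it removes controls from every safety table. It does need correcting, but doing so alone would produce a related-event column of 0 of 17, so both changes are needed.

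**The laboratory trigger in Protocol 7.1 is a weak asymmetry.** Controls cannot meet the limb about IP interruption, but they can meet the limb about medical or surgical intervention. It is real but minor.

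**Conclusion.** The point holds for the causality-filtered outputs. Because the grading refers only to the IP and controls receive none, the control column for treatment-related events is zero, or empty under the literal Safety population. A between-arm reading or test of that table is biased against Furoscix.

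The structural result follows from the definitions and needs no assumed rate. The size does: it rests on equal true rates in the two arms, full attribution on Furoscix and a Fisher test, none of which the documents state. Under those assumptions 8/34 against 0/17 is already nominally significant (p = 0.04).

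A reader might go further and conclude that the whole safety evaluation is biased by this rule. It is not. The all-causality, serious, special-interest and laboratory outputs do not use the grade. Those that run on the Safety population do need its definition corrected before they have a control arm. The change is worth making because it is specific and nearly free.

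**What to change.** 1. **Protocol 8.6 and SAP 15.3.1:** keep the IP-relatedness rating for serious adverse event reporting, but present IP-related events and causality for the Furoscix arm only, with no between-arm comparison or test.
2. **SAP 15.3:** state that between-arm safety comparisons use all-causality events counted from randomization. The treatment-emergent definition in SAP 9 and the documentation rule in Protocol 7.7.4 both start from dosing with study product, so they need a matching start point for controls.
3. **Protocol 8.2 and SAP 14:** amend the Safety population so that control subjects are included. Without this there is no control arm in the safety tables.
4. **Protocol 7.1 (minor):** make the laboratory trigger arm-neutral by referring to interruption or discontinuation of the assigned diuretic therapy instead of the IP. Do not add a change of therapy as a trigger, since that would widen the adverse event definition in both arms.

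The cost is wording in the SAP and a few protocol phrases. Restricting the table needs no new data. The related-event table loses its control column, which carries no information.

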7.7.1. Timeframes for Reporting SAEs

Prompt notification of the sponsor regarding SAEs is essential so that ethical and regulatory responsibilities and legal obligations can be satisfied. The Investigator must report SAEs according to the following time frames:

- Initial notification of all SAEs based on the available information must be provided to the sponsor or designee **within 24 hours** of the investigational site learning of the event. **(Initial notification within 24 hours of Death and life-threatening events is extremely important).**
 - Follow-up information when available must be sent to the sponsor or designee **within 48 hours** of receipt of the information by the investigational site.

7.7.2. SAE Information to Report

At a minimum, SAE reports must contain the Subject ID, the serious adverse event term, onset date, relationship to study product, and a brief narrative of the event. Please note that **relationship to study product/causality is very important** and must be included in the initial report as it may impact expedited regulatory reporting requirements for the event.

Copies of medical records will be requested. **However, it is not acceptable for the Investigator to send photocopies of the Subject's medical records in lieu of completion of the appropriate AE/SAE pages.** For medical records submitted, all Subject personal identifiers must be completely and thoroughly redacted prior to submission.

7.7.3. Clinical Laboratory Abnormalities and Other Abnormal Assessments as AEs and SAEs

The Investigator should exercise his or her medical and scientific judgment in deciding whether an abnormal laboratory finding, or other abnormal assessment is clinically significant.

Abnormal laboratory findings (e.g., clinical chemistry, hematology, and urinalysis) or other abnormal assessments (e.g., vital signs) that are judged by the Investigator as clinically

significant must be recorded as AEs or SAEs if they meet the definition of an adverse event. Clinically significant abnormal laboratory findings or other abnormal assessments that are detected after study product administration or that are present before study product administration but worsen after study product administration should be assessed for AE criteria.

